## 6. GENERAL CONSIDERATIONS

### 6.1. REFERENCE START DATE AND STUDY DAY

Study Day will be calculated from the reference start date and will be used to show start/stop day of assessments and events. Reference start date is defined as the day of the first dose of study drug, which is defined as Day 1.

Study Day will be computed as follows:

- Study Day = (Date of event – Date of first dose of study drug) + 1 if the date of the event is on or after the date of the first dose of study drug;
- Study Day = (Date of event – Date of first dose of study drug) if the date of the event is prior to the date of the first dose of study drug.

There is no Day 0. In the situation where the event date is partial or missing, Study Day and any corresponding durations will appear partial or missing in the listings.

### 6.2. BASELINE

Unless otherwise specified, baseline is defined as the last non-missing measurement taken prior to the first dose of study drug (including unscheduled assessments). In the case where the last non-missing measurement and the date and time of the first dose of study drug coincide, that measurement will be considered pre-baseline. In cases where the time is missing, and the last non-missing measurement and the date of the first dose of study drug coincide, that measurement will be considered pre-baseline.

Adverse event (AE) start date and time is to be collected. Any adverse event with start date and time prior to the date and time of first study drug administration will be considered as a baseline sign/symptom. An adverse event starting on the date of first dose of study drug with missing start time or with start time the same as or after the start time of the first study drug administration will be considered treatment-emergent, i.e. post-baseline.

Document:	\[REDACTED]\net\enterprise\Apps\sasdata\SASb\SAS\Atea_Pharmaceuticals\AT-527\ISZA63631\Biostatistics\Documentation\SAP\AT-03A-001_V1.0_COVID_SAP_PA7.doc		
Author:	\[REDACTED]	Version Number:	V1.0
		Version Date:	15Apr2021
Template No.:	CS_TP_BS016 Revision 6	Reference:	CS_WI_BS005

Effective Date: 02Dec2019

Copyright © 2009, 2010, 2012, 2016, 2018, 2019 \[REDACTED] All rights reserved. The contents of this document are confidential and proprietary to \[REDACTED] Holdings Inc. and its subsidiaries. Unauthorized use, disclosure or reproduction is strictly prohibited.

Medications starting on the date of first dose of study drug will be considered post-baseline.

## 6.3. UNSCHEDULED VISITS, RETESTS, AND EARLY TERMINATION DATA

For by-visit summaries, data recorded at the nominal visit will be analyzed. Unscheduled visits for safety labs and SARS-CoV-2 test will also be included in by-visit summaries (if they have been mapped to a scheduled visit following the rules provided in Table B of Section 6.4) and will contribute to the baseline timepoint and/or worst/maximum/minimum post-baseline value, where required (e.g. shift table).

In case of a retest when retest is defined as having blood sample tested twice, the latest available measurement for that blood sample will be used for the by-visit summaries. In case of a retest when retest is defined as having two blood samples collected on the same day, results from the last blood sample will be used for the by-visit summaries.

Refer to Section 6.4 for the conventions to map unscheduled and early termination data to protocol-defined visit windows. Early termination data might also contribute to the worst/maximum/minimum post-baseline value, where required (e.g. shift table).

Listings will include scheduled, unscheduled, retest and early discontinuation data.

## 6.4. WINDOWING CONVENTIONS

Early termination data will be mapped based on the scheduled Study Day of each scheduled visit as specified in the protocol schedule of events.

If early termination data are mapped to a scheduled visit for which data from the scheduled visit are also available (i.e., non-missing), the data collected at the scheduled visit will be used in the by-visit summaries. If early termination data are mapped to a scheduled visit for which data from the scheduled visit are not available (i.e., missing), data from the early termination visit will be used in the by-visit summaries.

Visits assigned as “unscheduled” by labs for safety data and SARS-CoV-2 test will be mapped based on the table below. If there is more than one unscheduled visit in a visit window, the visit closest to the target date will be used in by-visit analyses. If there is a tie between the numbers of days from the target date, the later visit will be used. Unscheduled visits that fall within the protocol-defined visit windows will be summarized in the by-visit analyses only if there is no scheduled visit available in the analysis visit window.

Document: \[REDACTED]\net\enterprise\Apps\sasdata\SASb\SAS\Atea\_Pharmaceuticals\AT-527\ISZA63631\Biostatistics\Documentation\SAP\AT-03A-001\_V1.0\_COVID\_SAP\_PA7.doc  
Author: \[REDACTED] Version Number: V1.0  
Template No.: CS\_TP\_BS016 Revision 6 Version Date: 15Apr2021  
Effective Date: 02Dec2019 Reference: CS\_WI\_BS005

Copyright © 2009, 2010, 2012, 2016, 2018, 2019 \[REDACTED] All rights reserved. The contents of this document are confidential and proprietary to \[REDACTED] Holdings Inc. and its subsidiaries. Unauthorized use, disclosure or reproduction is strictly prohibited.

**Table B: Analysis Visit Windows**

Scheduled Visit	Target Day of the Visit	Analysis Visit Window
Analysis visit windows for safety labs and SARS-CoV-2 Test		
Baseline	Day 1	Day -1 or Day 1/before 1 st dose
Day 2	Day 2	Day 2 to Day 3
Day 5	Day 5	Day 4 to Day 6
Day 8	Day 8	Day 7 to Day 9
Day 10	Day 10	Day 10 to Day 11
Day 12	Day 12	Day 12 to Day 13
Day 14	Day 14	Day 14 to Day 18
Day 21	Day 21	Day 19 to Day 25
Day 28	Day 28	Day 26 to Day 46
Day 63	Day 63	Day 47 to Day 79

## 6.5. COMMON CALCULATIONS

Change from baseline will be calculated as:

- Change from baseline = Test value at post-baseline visit – Baseline value

Percent change from baseline will be calculated as:

- Percent change from baseline (%) = (Change from baseline at post-baseline visit / Baseline value) X 100%

Document: \\[REDACTED]\net\enterprise\Apps\sasdata\SASb\SAS\Atea\_Pharmaceuticals\AT-527\SAZ\A63631\Biostatistics\Documentation\SAP\AT-03A-001\_V1.0\_COVID\_SAP\_PA7.doc  
Author: [REDACTED] Version Number: V1.0  
Template No.: CS\_TP\_BS016 Revision 6 Version Date: 15Apr2021  
Effective Date: 02Dec2019 Reference: CS\_WI\_BS005

Copyright © 2009, 2010, 2012, 2016, 2018, 2019 [REDACTED] All rights reserved. The contents of this document are confidential and proprietary to [REDACTED] Holdings Inc. and its subsidiaries. Unauthorized use, disclosure or reproduction is strictly prohibited.

## 7. STATISTICAL CONSIDERATIONS

For continuous data, descriptive statistics (i.e., n [number of subjects with available data], mean, standard deviation [SD], median, minimum, and maximum values) will be presented by treatment group and visit, when applicable.

For categorical data, the number and percentages of subjects in each category will be presented by treatment group and visit, when applicable

### 7.1. SAMPLE SIZE CALCULATION

The sample size calculation was based on these assumptions regarding the primary endpoint:

The primary endpoint for this study is the proportion of subjects with PRI, defined as a  $\geq$  2-tier increase in respiratory support methods required to maintain satisfactory oxygenation ( $\text{SpO}_2 \geq 93\%$ ), using the 6-tier hierarchical scale of Respiratory Support methods.

The primary efficacy goal is to reduce the incidence of PRI by 50% for active-dosed subjects compared to placebo recipients. The featured timeframe for this primary endpoint analysis will be the 14-day primary study period, with secondary analyses at study Days 10, 21, and 28.

With this study's relatively high-risk COVID-19 subject population (one or more known risk factors for poor outcomes), the study postulate is that 40% of placebo recipients will experience PRI during the 14-day study period, and the efficacy goal is therefore to reduce that incidence of PRI to 20% or less in active recipients.

Assuming PRI rates (PRIR) of 0.4 and 0.2 in the control and experimental arms, respectively, at alpha one-sided of 0.025, and at a power of 0.8, a total of 182 subjects are required at a 1:1 allocation, i.e. 91 per study arm. The study statistical hypotheses are as follows:

- $H_0: \text{Experimental}_{\text{PRIR}} \geq \text{Control}_{\text{PRIR}}$
- $H_a: \text{Experimental}_{\text{PRIR}} < \text{Control}_{\text{PRIR}}$

The key secondary endpoints will be tested, in order, only if the primary efficacy endpoint meets its success criteria, and each higher endpoint meets its success criteria. This hierarchical testing strategy will preserve study alpha.

First Key Secondary Efficacy Endpoint: Change from baseline in  $\log_{10}$  SARS-CoV-2 virus RNA. If 90% of patients have quantifiable viral load at baseline and the standard deviation for change from baseline  $\log_{10}$  viral load is 2

Document: \[REDACTED]\net\enterprise\Apps\sasdata\SASb\SAS\Atea\_Pharmaceuticals\AT-527\SAZ\A63631\Biostatistics\Documentation\SAP\AT-03A-001\_V1.0\_COVID\_SAP\_PA7.doc  
Author: \[REDACTED] Version Number: V1.0  
Template No.: CS\_TP\_BS016 Revision 6 Version Date: 15Apr2021  
Effective Date: 02Dec2019 Reference: CS\_WI\_BS005

## COVID-19 Statistical Analysis Plan

ATEA Pharmaceuticals  
Protocol AT-03A-001

Page 20 of 77

log10 copies/mL, then there is at least 85% power to detect a 1 log10 greater reduction in viral load using a two-sided level 0.05 test, i.e. a one-sided level 0.025 test. The corresponding statistical hypotheses are as follows:

- $H_0$ : Experimental change from baseline  $\geq$  Control change from baseline
- $H_a$ : Experimental change from baseline  $<$  Control change from baseline

Second Key Secondary Efficacy Endpoint: Median days to Clinical Recovery (MDCR), from randomization to a disease resolution status in the NIAID Clinical Status scale described in the protocol Section 6.9 - i.e. achieving Clinical Status 6, 7, or 8 by Day 14, according to whether the subject is still hospitalized at Day 14 or is an outpatient. Patients without observed clinical recovery will have clinical recovery time assigned as 15 days to preserve the ranks for the comparison.

The power assessment for this endpoint assumed days to clinical recovery in the control and experimental arms have exponential distributions. If the median time to recovery is 12 days for the placebo arm, then a one-sided 0.025 level test has 80% power to detect a 5 day reduction in median recovery time with the experimental arm (i.e. median is 7 days for experimental arm). If these assumptions hold, we would expect to observe approximately 50 and 68 clinical recoveries in the placebo and experimental arms, respectively, during the 14 day follow-up. The study statistical hypotheses are as follows:

- $H_0: \text{ExperimentalMDCR} \geq \text{ControlMDCR}$
- $H_a: \text{ExperimentalMDCR} < \text{ControlMDCR}$

### Third Key Secondary Efficacy Endpoint: Respiratory failure or death

The next key secondary efficacy endpoint of the study is the proportion of subjects with Respiratory Failure or Death (RFD), for which the featured assessment will be at Day 28, with additional analyses at Days 10, 14, and 63. Assuming the RFD rate (RFDR) is 0.35 and 0.15 in the control and experimental arms, respectively, at alpha one-sided of 0.025, at a total of 182 subjects with a 1:1 allocation, i.e. 91 per study arm, the power is 85%. The study statistical hypotheses are as follows:

- $H_0: \text{ExperimentalRFDR} \geq \text{ControlRFDR}$
- $H_a: \text{ExperimentalRFDR} < \text{ControlRFDR}$

Document: \\[REDACTED]\net\enterprise\Apps\sasdata\SASb\SAS\Atea\_Pharmaceuticals\VAT-527\ISZA63631\Biostatistics\Documentation\SAP\VAT-03A-001\_V1.0\_COVID\_SAP\_PA7.doc  
Author: [REDACTED] Version Number: V  
Template No.: CS\_TP\_BS016 Revision 6 Reference: CS\_WI\_BS016  
Effective Date: 02Dec2019

Copyright © 2009, 2010, 2012, 2016, 2018

Copyright © 2009, 2010, 2011  
Proprietary to [REDACTED] Holdings

Proprietary to [REDACTED] Holdings Inc. and its subsidiaries. Unauthorized use, disclosure or reproduction is strictly prohibited.

## 7.2. MISSING DATA

Missing efficacy data will be handled as described in Sections 16.1.2, 16.2.1.2, 16.2.1.2, 16.2.1.3 and 16.2.3.6 of this analysis plan.

Missing safety data will not be imputed, except for missing AE severity and relationship data (refer to Section 17.1.1). Partial or completely missing AE and medication dates will be handled as described in APPENDIX 1.

## 7.3. STATISTICAL TESTS

All statistical tests will be conducted at the two-sided 5% significance level (i.e. 2.5% for one-sided tests), unless otherwise specified in the description of the analyses. Confidence Intervals (CIs) will be two-sided with 95% coverage.

[figure not shown]
## 7.4. MULTIPLE COMPARISONS/ MULTIPLICITY

A sequential gatekeeping strategy will be utilized for the primary and the secondary efficacy endpoints to maintain the one-sided Type 1 error rate at  $\alpha=0.025$ . The efficacy objectives will be tested in the following order:

- (1) The primary efficacy endpoint of proportion of subjects with PRI in the ITT analysis set will be tested at one sided  $\alpha = 0.025$ .
- (2) If the primary efficacy comparison achieves statistical significance, there may be two comparisons for the first key secondary endpoint. The comparison at Day 5 will be tested first at one-sided  $\alpha=0.025$ . If statistical significance is met on the Day 5 comparison, then the quantitative SARS-CoV-2 changes at Day 2 would be formally tested at one-sided  $\alpha=0.025$ .
- (3) The second key secondary endpoint of median days to clinical recovery will be tested at one sided  $\alpha = 0.025$  only if the primary efficacy objective and the first key secondary objective are met for Day 5 and Day 2 (at one-sided  $\alpha=0.025$ ).
- (4) The final key secondary endpoint of proportion of subjects with respiratory failure or death will be tested at one sided  $\alpha = 0.025$  only if both the primary efficacy objective and the first and second key secondary objectives are met (at one-sided  $\alpha=0.025$ ).

Document: \[REDACTED]\net\enterprise\Apps\sasdata\SASb\SAS\Atea\_Pharmaceuticals\AT-527\SAZ\A63631\Biostatistics\Documentation\SAP\AT-03A-001\_V1.0\_COVID\_SAP\_PA7.doc  
Author: \[REDACTED] Version Number: V1.0  
Template No.: CS\_TP\_BS016 Revision 6 Version Date: 15Apr2021  
Effective Date: 02Dec2019 Reference: CS\_WI\_BS005

Copyright © 2009, 2010, 2012, 2016, 2018, 2019 \[REDACTED] All rights reserved. The contents of this document are confidential and proprietary to \[REDACTED] Holdings Inc. and its subsidiaries. Unauthorized use, disclosure or reproduction is strictly prohibited.

Only nominal two-sided p-values will be provided for the other secondary and the exploratory efficacy endpoints.

No statistical testing will be performed for the safety endpoints.

## 7.5. MULTICENTER STUDIES

This study will be conducted by multiple investigators at multiple centers. Data from all centers will be pooled together in the analyses and there are no plans to perform an analysis of homogeneity of the results across centers.

## 7.6. ADJUSTMENTS FOR COVARIATES AND FACTORS TO BE INCLUDED IN ANALYSES

The analyses will be adjusted for the following covariates and factors.

- Geographic regions (stratification variable for randomization)
  - North America
  - South America
  - Europe
  - Rest of World
- Baseline quantitative SARS-CoV-2 (virologic endpoints only)

If data are too sparse for one level of the Geographic region factor (i.e., less than 5% of subjects), South America and Rest of World will be combined. If the level is still less than 5% of subjects, then the factor will not be included in the statistical model/test. Determination of the factor(s) to be included into the statistical models/tests will be finalized before the study DBL in a blinded fashion.

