8. STATISTICAL ANALYSES

This section summarizes the statistical analyses pertinent to the efficacy and safety assessments in this study. A statistical analysis plan (SAP) describing the detailed statistical methods for this study will be prepared and finalized before database lock. Sample size calculations and power

Protocol Number: AT-03A-001

statements, with the exception of those for time to Clinical Recovery, were performed using SAS/STAT v9.4 (SAS Institute Inc., Cary, NC, USA). The power estimates for time to Clinical Recovery were computed by simulation. Corresponding code is provided in [Section 13](#).

All analyses of trial data will be performed in this version of SAS/STAT or higher unless noted in the eventual SAP that other software will be utilized.

This is a double-blind randomized study, with variable size block randomization stratified by region.

In order to support interactions with regulatory agencies, the Sponsor may choose to conduct interim analyses during the course of the study. The decision to conduct an interim analysis and the timing of the analysis will be documented in the Sponsor's trial master file prior to the conduct of the interim analysis. The interim analysis will be performed and interpreted by members of the Sponsor study team and appropriate senior management personnel, who will be unblinded at the treatment group level.

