8.3. Efficacy Analysis Methods

8.3.1. Primary Efficacy Analysis

Part A

The ITT population will be the primary efficacy analysis population for Part A. Proportions of subjects (active or placebo-treated) with PRI until study completion (Day 14) will be compared by study arm. The Cochran Mantel Haenszel (CMH) test will be performed to compare the proportion of PRI rate in study arms. Stratification variables will include the randomization strata of geographic regions; additional stratification variables may be described in the eventual SAP, to be finalized prior to database lock.

Part B

Viral load will be assessed quantitatively using a validated assay. The analyses will compare change from baseline log10 viral load at each required scheduled timepoint. The analyses will be carried out on the mITT population. Change from baseline viral load will be compared between the AT-527 group and the placebo group at required post-baseline timepoint using ANCOVA with treatment as a factor and log10 baseline viral load as a covariate. The least squares mean (LSM) change and its standard error of means (SE) in each group, the differences between two groups in LSM change with corresponding 95% confidence intervals (CIs), and p-values will be presented.

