### 16.1.3. PRIMARY ANALYSIS OF PRIMARY EFFICACY ENDPOINT

The primary efficacy goal is to reduce the incidence of PRI by 50% for active-dosed subjects compared to placebo recipients. Number and proportion of subjects with and without PRI during the 14-day primary study period will be provided by treatment group based on the ITT analysis set. The difference between the treatment groups will be presented with corresponding 95% CI. A Cochran-Mantel-Haenszel (CMH) general association test will be used to test for differences in rates between the treatment groups controlling for geographic region (see [Section 7.6](#)).

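### SAP 7.6 has no working remedy for a sparse North American or European region; read plainly, it then removes region from the CMH test that the protocol stratifies by region

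*SAP*

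**What the plan says.** Protocol section 8 describes the randomisation: "This is a double-blind randomized study, with variable size block randomization stratified by region". No other stratum is named. Protocol 8.3.1 specifies a CMH test for the Part A primary endpoint: "Stratification variables will include the randomization strata of geographic regions". It lets the SAP add stratification variables but makes no provision for removing region. The synopsis likewise adjusts the test for the randomisation strata. SAP 16.1.3 agrees: the CMH test "will be used to test for differences in rates between the treatment groups controlling for geographic region".

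SAP 7.6 lists four levels (North America, South America, Europe, Rest of World) and adds a sparse-data rule in two steps. The trigger is "If data are too sparse for one level of the Geographic region factor (i.e., less than 5% of subjects"). The first step is "South America and Rest of World will be combined". The second is "If the level is still less than 5% of subjects, then the factor will not be included in the statistical model/test". The decision is to be "finalized before the study DBL in a blinded fashion".

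**The concern.** The trigger covers all four regions but the remedy reaches only two. If South America or Rest of World is small, merging them may cure it. If North America or Europe is small, the merger leaves that share as it was, and the second step then appears to discard the whole factor. The same degree of sparsity gives opposite outcomes depending only on which region is small.

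At stake is whether the primary test is analysed by the groups it was randomised by, as the protocol says. The CMH test does not need the factor removed, because a very small stratum carries little weight and does no harm.

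**Working it through.** **Inputs.** From the documents: the 5% threshold and the two-step rule (SAP 7.6); 81 subjects randomised in Part A (Protocol 3.1 and 3.2); a planned 182, with PRI of 0.4 on placebo and 0.2 on active, one-sided alpha 0.025 and power 0.8 (SAP 7.1). Assumed, because the documents do not give them: subjects per region and PRI rates by region.

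**1. The plan's own figure.** The region rule has no calculated figure beyond 5%. The sample size that the CMH test serves does reproduce.
- Uncorrected: n = (1.96 × √(2 × 0.3 × 0.7) + 0.842 × √(0.24 + 0.16))² / 0.2² = 81.2 per arm, so 82 per arm, or 164 in total.
- With continuity correction: (81.2/4) × (1 + √(1 + 4/(81.2 × 0.2)))² = 90.9, so 91 per arm, or 182 in total.
- Exact Fisher power at 91 per arm is 0.808.

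**2. What triggers the rule.** 4/81 = 4.9% and 5/81 = 6.2%, so 4 or fewer subjects trigger it in Part A. At 182 it is 9 or fewer (9/182 = 4.9%).

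**3. The rule applied to 81 subjects (illustrative counts).**

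| N. America | S. America | Europe | Rest of World | After merger | Region, plain reading |
|---|---|---|---|---|---|
| 4 | 30 | 30 | 17 | S. America + Rest of World 47/81 = 58.0%; N. America still 4.9% | dropped |
| 30 | 30 | 4 | 17 | S. America + Rest of World 58.0%; Europe still 4.9% | dropped |
| 30 | 4 | 30 | 17 | S. America + Rest of World 21/81 = 25.9% | kept |

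If the level in the second step means the merged level, region stays in all three cases. North America or Europe then remains below 5% in the first two, and no rule applies to it.

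**4. Information lost by dropping region.** Take two equal-sized regions with PRI rates p1 and p2. The within-region variance is the mean of p(1−p). The variance ignoring region is m(1−m), where m is the mean rate. The ratio is the share of information kept.
- p1 = p2: ratio 1, no loss.
- 2% and 8%: (0.0196 + 0.0736)/2 = 0.0466; 0.05 × 0.95 = 0.0475; ratio 0.98, about 2% lost.
- 5% and 30%: (0.0475 + 0.2100)/2 = 0.1288; 0.175 × 0.825 = 0.1444; ratio 0.89, about 11% lost.

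**5. Power and type I error by simulation.** There were 40,000 trials per row, allocated 1:1 within region, with a common odds ratio of (0.2/0.8)/(0.4/0.6) = 0.375. Region sizes were 8, 60, 68 and 46 (N = 182) or 4, 30, 30 and 16 (N = 80, standing in for 81). The sparse and the last region have a placebo rate of 0.4; the two large ones have the rates shown. Merging joins the sparse region to the second one.

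| N | Rates in the two large regions | Power: four strata | Power: sparse merged | Power: region dropped | One-sided type I error: four strata | One-sided type I error: dropped |
|---|---|---|---|---|---|---|
| 182 | 0.4, 0.4 | 0.844 | 0.844 | 0.847 | 0.026 | 0.026 |
| 182 | 0.3, 0.5 | 0.845 | 0.844 | 0.841 | 0.027 | 0.024 |
| 182 | 0.2, 0.6 | 0.824 | 0.823 | 0.795 | 0.026 | 0.019 |
| 182 | 0.1, 0.7 | 0.771 | 0.768 | 0.687 | 0.024 | 0.010 |
| 80 | 0.4, 0.4 | 0.499 | 0.502 | 0.497 | 0.027 | 0.027 |
| 80 | 0.2, 0.6 | 0.468 | 0.465 | 0.415 | 0.025 | 0.019 |
| 80 | 0.1, 0.7 | 0.415 | 0.410 | 0.304 | 0.024 | 0.010 |

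Merging costs at most about 0.6 points of power (0.4153 − 0.4096). Dropping region costs nothing when rates are equal, 3 to 5 points at 0.2 and 0.6, and 8 to 11 points at 0.1 and 0.7. It makes the test conservative when rates differ.

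**The case against.** Five things can be said for the plan.

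- **The wording is ambiguous.** The second step directly follows the merger, so the level may be the merged one, and a small North America or Europe would then not remove region. This stands as a possible reading. It exchanges one defect for another, because the SAP would then be silent on that case.
- **The reach is narrow.** The viral-load ANCOVA, the Wilcoxon test and the log-rank tests name no region term in their own sections. The Changes to Planned Statistical Analyses Form of 16 March 2022 leaves out respiratory failure or death, mortality, PCR positivity and all PRI sensitivity analyses except mITT. This stands. A reader might infer that every planned test would lose its stratification; the documents do not support that.
- **The loss may be trivial.** The protocol reports a low overall PRI rate, which favours the small end of the range. This stands. A reader might take 11% as the expected loss, but no regional rates are given to support any single figure.
- **The decision is blinded and precedes database lock.** This stands, and it protects against a choice steered by results. It does not give the rule a remedy that it lacks.
- **Little depends on the test.** The sponsor concedes that a PRI effect cannot be shown, and Protocol 8.2.2 calls all analyses descriptive. This stands and keeps the point minor.

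Two further inferences should be resisted. One is that the PRI test was in fact run without strata: enrolment by region is not reported, so this cannot be known. The other is that dropping region makes false positives more likely: the simulation shows type I error equal to or below that of the stratified test.

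**Conclusion.** The point holds as a minor defect in the rule. On the plain reading, a North American or European share below 5% removes the only randomisation stratum from the region-controlled CMH analyses, contrary to Protocol 8.3.1. On the other reading, that situation has no rule. Either way the sentence needs repair.

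The consequence is lost precision and a conservative test. The loss ranges from about zero to about 11% of the information over the regional rates considered, all of which are assumptions. The larger power losses in the simulation need wide regional differences around the planned 40% placebo rate, well above what the protocol says was seen. The analyses affected in the final outputs are essentially PRI in ITT and mITT.

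**What to change.** Replace the two-step rule in SAP 7.6 with the following:

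- Region is retained in every CMH test.
- If South America or Rest of World has under 5% of subjects, the two are combined.
- If North America or Europe has under 5%, that level is combined with Rest of World, or with the combined South America/Rest of World level where those two have already been merged.
- Any level still below 5% is kept as its own stratum. The factor is not dropped.

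This covers each region, including a sparse Rest of World, and leaves no choice to be made later. It costs a few lines of SAP text, needs no extra data, and costs next to no power.

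The March 2022 form says that the SAP will not be revised and that the interim outputs serve as the final ones. For this study the practical step is therefore in the report: give the number of subjects per region and state which strata the PRI CMH test used in ITT and mITT. If region was dropped, show the region-stratified result beside it, labelled as post hoc.
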